This study will recruit women attending collaborating clinics and women from the communities surrounding those clinics. Three groups will be recruited:

- 757 HPV-vaccinated WLWH (Group 1),
- 757 HPV-unvaccinated WLWH (Group 2), and
- 757 HIV[-] women who are HPV-vaccinated (Group 3)
- 757 HIV[-] women who are HPV-unvaccinated (Group 4)

Within the HPV-vaccinated groups 1 and 3, the study will recruit at least 274 women with three doses and 274 women with two doses, with the remaining 209 will not be selected by the number of doses and may have 2 or 3 doses. The number of doses of HPV vaccination a woman received is dictated by introduction of HPV vaccination in Rwanda as previously shown in **Table 1**. In general, most Rwandan women born in 2003 or later will have been vaccinated with two doses of Gardasil®, women born between 1996 and 2002 will have been vaccinated with three doses of Gardasil®, and women born in 1995 or earlier will be unvaccinated.

Table 3. Target population by HIV status and age

HIV Status	Approximate number of HPV vaccine doses	Birth year	Age at year of study enrollment (years)		N
			in 2021	in 2023	
WLWH	3 doses	1996-2002	19-25	21-26	274
	2 doses	2003-2005	16-18*	18-20	274
	2 or 3 doses	1996-2005	19-25	18-26	209
	0 doses - unvaccinated	1993-1995	26-30*	28-31*	757
HIV[-]	3 doses	1996-2002	19-25	21-26	274
	2 doses	2003-2005	16-18*	18-20	274
	2 or 3 doses	1996-2005	19-25	18-26	209
	0 doses- unvaccinated	1993-1995	26-30*	28-31*	757
TOTAL					3,028

*Only women age 18-28 are eligible for enrollment.

Therefore, we will recruit by age, which will serve as a useful and very good proxy for HPV vaccination status, which otherwise would be difficult to confirm in real time at enrollment. HPV vaccination status then will be confirmed by retrospective review of the HPV vaccination records kept by the Rwanda Ministry of Health (MoH), who are collaborating on this project. The number of women recruited will therefore be stratified by age (as proxy for vaccine status) and HIV status (**Table 3**).

VI.D. Eligibility Criteria

VI.D.1 Inclusion Criteria

1. Gender: Female
2. Age: 18-28 years. The age of inclusion criteria will likely be restricted as age-specific enrollment goals are met.
3. Physically and mentally able and willing to participate in the study.
4. Willing to provide written and signed or thumb printed, informed consent.

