All histopathology slides will be scanned at the study lab and reviewed by two local pathologists and the Einstein study pathologist (105). If the diagnoses are concordant, no further review of the case will be performed. If the diagnosis is discordant and at least one pathologist diagnoses CIN2+, the biopsy slide will be subjected to a joint review and consensus diagnosis. For Negative/cervical intraepithelial neoplasia grade 1 pairs of diagnoses, which does not influence our analyses or the care of the participants, there will be no joint review.

VII. STATISTICAL SECTION

VII.A. Specific Aim 1

To measure population effectiveness of prophylactic HPV vaccine in reducing cervicovaginal, anal, and/or oral prevalent and persistent infections by HPV6/11/16/18.

VII.A.1. Analyses.

We will calculate the point prevalence and the prevalence of persisting infection by individual HPV-type specific infections, with binomial 95% confidence intervals (95% CI), for each anatomic and for the woman (all anatomic sites) for Gardasil®-vaccinated WLWH, Gardasil®-vaccinated HIV[-] women, unvaccinated WLWH and unvaccinated HIV[-] women. We likewise will calculate the point prevalence and the prevalence of persisting infection with 95%CI for all

HPV types in aggregate and in sub-groups of HPV types according to the protection afforded by Gardasil®: Gardasil®-targeted types (HPV6, 11, 16, and 18), Gardasil®-untargeted types for which there might be cross-protection (HPV31, 33, and 45) (40, 106, 107), and Gardasil®-untargeted HPV types for which there is little or no evidence of cross-protection (HPV35, 39, 51, 52, 53, 56, 58, 59, 66, and 68). Results will be stratified by age and number of doses (3 vs. 2) as well as other factors possibly associated with HPV prevalence. Differences in the prevalence of these HPV type sub-groups (targeted, possible cross-protection, and untargeted) between the four study groups of women will be tested using Fisher's exact or Pearson chi-square test. Differences in the prevalence of these HPV type subgroups by age, number of doses (3 vs. 2), and other factors within the group, will be tested for statistical significance ($p<0.05$) using a Fisher's exact or Pearson chi-square test.

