Notably, the study groups of participants are fundamentally different populations (vs. a randomized control trial that would recruit from the same population and, as result of randomization, enroll similar, representative populations in each arm). Specifically, there are known differences in age (and therefore possible differences sexual behaviors) between Gardasil®-vaccinated vs. -unvaccinated WLWH, and possible differences in sexual behaviors between Gardasil®-vaccinated WLWH vs. HIV[-] women (since HIV infection predominately is sexually transmitted in this population). Therefore, we will use a relative measure of effectiveness to account for the differences in age and possible differences in exposure to HPV. We will use logistic regression to calculate the odds ratio (OR) of the point prevalence and the prevalence of persisting HPV infections of Gardasil®-targeted HPV types, individually (HPV6, 11, 16, or 18) and in aggregate (HPV6, 11, 16, and 18), vs. untargeted HPV genotypes for which there is no evidence of cross-protection, for each anatomic site individually (cervix, anus, OR oral cavity) and combined (cervix, anus, AND oral cavity). That is, we will compare the ratio between study groups of participants as follows:

$\frac{N_{HPV6/11/16/18}}{N_{HPV35/39/51/52/53/56/58/59/66/68}}$ [vaccinated WLWH] (Group 1)
 $\frac{N_{HPV6/11/16/18}}{N_{HPV35/39/51/52/53/56/58/59/66/68}}$ [unvaccinated WLWH] (Group 2)
 or

$\frac{N_{HPV6/11/16/18}}{N_{HPV35/39/51/52/53/56/58/59/66/68}}$ [vaccinated WLWH] (Group 1)
 $\frac{N_{HPV6/11/16/18}}{N_{HPV35/39/51/52/53/56/58/59/66/68}}$ [vaccinated HIV[-] women] (Group 3)

or

$\frac{N_{HPV6/11/16/18}}{N_{HPV35/39/51/52/53/56/58/59/66/68}}$ [vaccinated HIV[-] women] (Group 3)
 $\frac{N_{HPV6/11/16/18}}{N_{HPV35/39/51/52/53/56/58/59/66/68}}$ [unvaccinated HIV[-] women] (Group 4)

This will allow us to account for differences in HPV exposure, prevalence, and persistence due to differences in age (n.b., prevalence equals incidence * duration; prevalent infections at older ages tend to be more persistent ((108)) and sexual behaviors between groups. Additional logistic regression models may be used to adjust specifically on other factors, including age, number of doses, and sexual behaviors, to account for population differences between study groups.

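### The only committed Aim 1 test of three versus two vaccine doses is a crude prevalence test, and because birth year sets the dose, it cannot separate a dose effect from age and HPV exposure

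*Combined protocol and SAP*

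**What the plan says.** Section VII.A.1 (Analyses, Specific Aim 1) makes two statements about dose. The first is descriptive: "Results will be stratified by age and number of doses (3 vs. 2) as well as other factors possibly associated with HPV prevalence". The second is a significance test at p<0.05, within each study group, whose subject is "Differences in the prevalence of these HPV type subgroups by age, number of doses (3 vs. 2), and other factors within the group". The stated method reads "using a Fisher's exact or Pearson chi-square test". No covariates are attached to that test.

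Section VI.C explains where dose comes from: "The number of doses of HPV vaccination a woman received is dictated by introduction of HPV vaccination in Rwanda". It adds, as a broad rule, that "most Rwandan women born in 2003 or later will have been vaccinated with two doses of Gardasil®, women born between 1996 and 2002" had three doses. Table 3 gives birth years 1996-2002 for three doses and 2003-2005 for two, with ages 21-26 and 18-20 in 2023. Each vaccinated group is to include "at least 274 women with three doses and 274 women with two doses", plus 209 women not selected by dose.

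Further on in VII.A.1 the plan says that its study groups differ in age and possibly in sexual behaviour. It therefore states that "we will use a relative measure of effectiveness to account for the differences in age and possible differences in exposure to HPV". That measure is the ratio of HPV6/11/16/18 to ten untargeted types, and it is written out for three contrasts: Groups 1 v 2, 1 v 3 and 3 v 4. Extra logistic models with age, number of doses and sexual behaviour are mentioned as something that may be used, and their purpose is given as differences between study groups.

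**The concern.** The plan names the confounding and provides a tool for it, but does not apply the tool to three v two doses. In that contrast age and exposure are tied to the comparison at least as tightly as elsewhere, because programme year fixes both dose and birth cohort. A significant crude result could come from dose, from age-related exposure, or from both. A null result could be a real dose difference cancelled by exposure. The crude test on untargeted types could also return a significant result by dose for types that the vaccine does not cover, and the plan has no rule for reading it.

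At stake is any statement about infection under two doses compared with three, in women living with HIV or in HIV-negative women.

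**Working it through.** **No stated figure to reproduce.** The documents give no power, sample size or effect size for the Aim 1 dose contrast. The check is how the planned test behaves when dose has no effect.

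**Inputs from the documents**
- Women per dose, in each vaccinated group: at least 274 (VI.C). If the other 209 split evenly, 274 + 209/2 ≈ 378.
- HPV prevalence 30%, of which 25% targeted and 55% untargeted (VII.A.2): 0.30 × 0.25 = 7.5% and 0.30 × 0.55 = 16.5% of women.

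**Assumptions**
- Exposure ratio between the dose cohorts: 1.5, acting equally on all types. The documents give no value.
- The test is two-sided; the plan does not say.
- The 7.5% makes no allowance for vaccination, yet both dose groups are vaccinated. A second value of 3.75% (half) is used, in line with the odds ratio of 0.5 in VII.A.2.

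**Step 1: crude test, no dose effect.** Two-dose prevalence = three-dose prevalence / 1.5. Exact rejection rates of Fisher's test at 0.05:

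| Types | Three-dose | Two-dose | Crude OR | 274 per dose | 378 per dose |
|---|---|---|---|---|---|
| Targeted, halved | 3.75% | 2.5% | 1.52 | 9% | 12% |
| Targeted | 7.5% | 5.0% | 1.54 | 17% | 25% |
| Untargeted | 16.5% | 11.0% | 1.60 | 42% | 56% |

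With equal group sizes the test is symmetric. Swapping the columns, so that the two-dose women have the higher prevalence, gives the same rates in the other direction. The result also depends on where the 7.5% is anchored. Placed on the two-dose women (7.5% v 11.25%), the normal-approximation rejection rate for the two-proportion test is 33% at 274 per dose.

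**Step 2: masking.** Crude prevalence ratio = true ratio × exposure ratio. A true ratio of 0.70 for three doses with an exposure ratio of 1.43 gives 0.70 × 1.43 = 1.00, which is no visible difference.

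**Step 3: why age stratification does not help.** Birth years 1996-2002 and 2003-2005 do not overlap. At any one date the two age ranges at most meet at the edge, so almost no age stratum holds women of both doses.

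**Step 4: the plan's own ratio applied to dose.** In a simulation with 274 per dose, no dose effect and exposure ratios from 1.0 to 2.0, the chi-square test of targeted against untargeted infections rejected in 3-4% of runs. This is largely by construction, because one multiplier acts on both type classes. It shows that the ratio removes this form of bias, not every form.

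**Step 5: what the ratio costs.** Informative women per dose stratum: 274 × 0.30 × (0.25 + 0.55) ≈ 66. Targeted share in the reference stratum: 0.25/0.80 = 31.25%. At OR 0.5 the odds are 0.5 × 0.3125/0.6875 = 0.227, a share of 18.5%. Power to separate 31.25% from 18.5% with 66 per stratum is about 39%. Persistent infection leaves fewer still: 66 × 0.90 × 0.70 ≈ 41, using the loss and persistence assumptions in VII.A.2.

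**The case against.** A reader might infer that the crude test will show more HPV6/11/16/18 in three-dose women simply because they are older. The documents do not support that. The outcome is current infection, not cumulative exposure. Section VII.A.2 puts the prevalence peak about 5 years after median sexual initiation, and section I.B gives that median as typically 15-17 years, so the peak lies at about 20-22. Two-dose women (18-20) are mostly approaching it; three-dose women (19-26) straddle and pass it. Women with no sexual activity are excluded (VI.D.2), which narrows the exposure gap. The bias could be small or reversed. What stands is that the two explanations cannot be separated.

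A reader might also infer that infection by dose is a headline question. The Executive Summary and X.A.1 place the 2015 switch in the sentence on immune response, and the 274 per dose matches the titre power calculation in VII.B.2. For titres, VII.B.1 does plan models with age at vaccination, age at enrolment and number of doses. This lowers the importance of the Aim 1 contrast, but VII.A.1 still commits to a significance test of infection by dose.

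The plan is not silent on the bias. Section XI lists the three-dose and two-dose cohorts among its differing populations and concedes that age bias cannot be fully controlled. The questionnaire (Appendix III) collects lifetime partners and age at first sex, which birth year does not fix, and the optional models could use them. Testing untargeted types by dose could serve as a negative control. None of this is committed for the dose contrast.

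**Conclusion.** The point holds as a gap in the analysis plan: the one committed Aim 1 dose test is unadjusted, dose is set by birth cohort, and the plan's remedy is not extended to it. The rejection rates in the working illustrate how far a 1.5-fold exposure difference could move the test from its nominal 5%; they do not forecast this study. They rest on an assumed ratio, an assumed direction and an assumed targeted prevalence in vaccinated women, and they change materially with the last of these. The contrast is secondary within Aim 1 and has no power statement. The change is worth making because it is cheap and uses a method already in the plan. The main Aim 1 comparisons are not affected.

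**What to change.** In VII.A.1, add a fourth contrast to the list of ratios: the targeted:untargeted odds ratio for three v two doses, within Group 1 and within Group 3, for prevalent and for persistent infection. Name it as the inferential dose comparison. Keep crude prevalences by dose, with confidence intervals, as description. State that the comparison of untargeted types by dose is read as a negative control: a difference there points to confounding, not to a dose effect. Whether a p-value is also printed beside the crude prevalences is a matter of preference.

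The cost is wording; the data and the model are already planned. Two limits should be stated with it. Power is low, about 39% for a prevalence odds ratio of 0.5 and less for persistence, so a null result should not be read as equal protection. The ratio also does not remove differences in age at vaccination (some three-dose women were vaccinated in the catch-up at about 15 years, section I.D) or in time since vaccination. Both track dose and can act on targeted types alone.

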The natural history of HPV and cervical carcinogenesis can be represented by a simple, causal schema of four, reliably measured stages (22): 1) HPV acquisition, 2) HPV persistence, 3) progression to precancer (CIN3/AIS), and 4) ICC. The key step in cervical carcinogenesis is overt, measurable HPV persistence, which even after a year or two strongly predicts the development of cervical precancer and cancer (i.e., CIN3 or more severe diagnoses) (CIN3+) (23). HIV co-infection has a profound impact on the natural history of HPV, thereby increasing the risk of ICC. HIV co-infection increases the 1) likelihood of cervical and anal HPV persistence and 2) likelihood of cervical and anal HPV infections progressing to precancer (24, 25). Incident HIV infection also significantly increases the risk of newly detected cervical and anal HPV infection, presumably due in part to immune dysregulation resulting in increased persistence of even transient infections (prevalence = incidence * duration) and/or and re-activation of a latent/well-controlled HPV infection (25).

Meta-analyses of HIV/AIDS cohorts reported a 6-fold increased incidence of cervical cancer compared to the general female population/HIV[-] women (26). Unexpectedly, despite the introduction of combined anti-retroviral therapy (ART) and concomitant immune reconstitution, the incidence of the HPV-related malignancies, notably cervix and anal carcinomas, has not decreased as they have for other malignancies (e.g., Kaposi sarcoma and specific types non-Hodgkin lymphoma i.e., Burkitt Lymphoma, Immunoblastic Lymphoma, and primary lymphoma of the brain) and may have increased. This increase is perhaps the result of HIV-infected patients living longer (27, 28), long enough to develop HPV-related cancers (29, 30).

I.B. Prophylactic HPV Vaccination

The discovery of high-risk HPV (hrHPV) infections as the necessary cause of cervical cancer has led to revolutionary advances in cervical cancer prevention, including the development of prophylactic HPV vaccines for primary prevention. Current prophylactic HPV vaccines are based on the self-assembly of recombinantly expressed L1 protein in cell lines into virus-like particles (VLPs) that resemble native viral capsids but without the viral genome necessary for viral replication.

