Similarly, exploratory analyses will compare the effectiveness of HPV vaccination for cross-protection types and endpoints of cumulative detection of Gardasil®-targeted HPV types-associated CIN2+ and/or anal intraepithelial neoplasia grade 2 or more severe (AIN2+) (vs. untargeted HPV type-associated CIN2+ and/or AIN2+) between study groups.

For participants in the existing IeDEA database we will extract HIV specific variables. For those who we cannot match to the IeDEA database, will extract HIV specific variables from medical records.

In another exploratory analysis, among WLWH, the presumed route of HIV acquisition (either maternal to child or behavioral) will be compared with HPV positivity and, among HPV-positive women, HPV viral load.

VII.A.2. Sample Size/Power for Gardasil®-vaccinated vs. unvaccinated WLWH.

For this analysis, we will make the following assumptions: 1) at least 30% prevalence of HPV infection (of any anatomic site) at baseline, 25% of which will be Gardasil®-target HPV types and 55% will be untargeted HPV types, 2) a 10% loss to follow-up (LTFU) in at follow up visit, and 3) at least 70% of HPV infections persist for 6-12 months. We justify an HPV prevalence of at least 30% based on 30% prevalence of high-risk HPV infection of the cervix in 30-year-old WLWH from our previous U54 study (109). We expect that the HPV prevalence may be higher since the prevalence of HPV, like that of other sexually transmitted infections, tends to peak about 5 years after the median age of sexual initiation in a population. However, we conservatively used 30% to ensure adequate statistical power. We justify our assumption of a maximum of 10% follow-up, given our experience working in Rwanda over the last ~20 years. We justify 70% of prevalent HPV infections persisting for 6-12 months, given that 36-50% of prevalent HPV infections persist 6-months in HIV[-] women (109, 110) and WLWH have an impaired immunity to HPV (8, 9).

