Sample size calculation relates to the relative effectiveness measure as discussed. Under above assumptions, a sample size of 757 vaccinated and 757 unvaccinated WLWH will provide $\geq 80\%$ power ($p=0.05$) to detect an OR of ≤ 0.5 for 6-12 month persistent HPV6/11/16/18 infections, relative to HPV35/39/51/52/53/56/58/59/66/68 (but not HPV31/33/45 because of possible cross protection), in Gardasil®-vaccinated vs. -unvaccinated WLWH. Consequently, because there will be more participants with a prevalent infection than 6-12 month persistent HPV infection (because there are no losses to follow-up or HPV viral clearance for which to account), there will

be $\geq 80\%$ power ($p=0.05$) to detect a OR of ≤ 0.75 in point prevalence of HPV6/11/16/18 infection relative to HPV35/39/51/52/53/56/58/59/66/68, in Gardasil®-vaccinated vs. - unvaccinated WLWH.

VII.B. Specific Aim 2

To quantify, and examine the determinants of, long-term antibody responses to, HPV vaccination.

VII.B.1. Analyses.

Geometric mean titers (GMT) and seropositivity (seroconversion) will be compared between 1) HPV-vaccinated WLWH and HPV-vaccinated HIV[-] women, overall and stratified on the number of vaccine doses, 2) HPV-vaccinated and unvaccinated WLWH, overall and by the number of doses received by the HPV-vaccinated WLWH, and 3) three vs. two doses for HPV-vaccinated WLWH and 4) HPV-vaccinated and unvaccinated HIV[-] women, overall and by the number of doses received by the HPV-vaccinated HIV[-] women.

Differences in GMT and seropositivity will be tested for statistical significance using the Mann-Whitney and Fisher's exact tests, respectively. ANOVA and logistic regression models will be used to adjust for/assess the association of other factors (e.g., age at vaccination, age at enrollment into the study, number of doses, HIV status [positive vs. negative and current antiretroviral therapy, CD4 counts, and HIV viral load] and history [e.g., CD4 nadir], and detection of HPV genotypes, etc.) with GMT and seropositivity, respectively.

Among vaccinated and unvaccinated HPV seropositive WLWH, the association between HPV antibody titer and presumed route of HIV acquisition (either maternal to child or behavioral) will be examined.

VII.B.2 Sample Size/Power to compare Gardasil®-vaccinated WLWH vs. Gardasil®-vaccinated HIV[-] women.

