The Rwandan staff, which has extensive experience working in this community, is very knowledgeable about the population. We will be able to work with and through RD Rwanda and RMH, the Advisory board, and the community health workers to ensure that a representative population of WLWH and the community surrounding the health clinic is recruited into the study. As part of the training for the study, we will make certain that the clinical team recruits without bias.

IX.I. Staff

The staff is already receiving the necessary training during our previous U54 grant (5U54CA190163) to conduct this study. However, we are allocating several months for protocol development and staff training before enrollment starts. The local staff will be responsible for providing most of the clinical services and increasingly so as they get additional training.

X.PROTECTION OF HUMAN SUBJECTS

X.A. Risks to Human Subjects

X.A.1. Human Subjects Involvement, Characteristics, and Design

This is an observational study to assess the long-term population effectiveness and immunity of the HPV vaccine (Gardasil®) in Rwandan WLWH. The study will compare the cervicovaginal, anal, and oral prevalent and 6-12 month persistent HPV6/11/16/18 infections in HPV-vaccinated WLWH to those in unvaccinated WLWH and HPV-vaccinated HIV[-] women. We will also compare the HPV immune response in HPV-vaccinated WLWH to HPV-vaccinated HIV[-] women and the impact of switching from 3 doses to 2 doses of Gardasil® in 2015. Finally, the study will investigate the risk factors, including the CVM, for HPV persistence in WLWH. The long-term goal is to establish a cohort of WLWH in whom we can examine the long-term effectiveness of HPV vaccination in WLWH now and in the future.

The study will include 757 WLWH and 757 HIV[-] women who did receive vaccination (birth cohorts 1996 and later) and 757 WLWH who did not receive HPV vaccination (birth cohorts before 1996) and 757 HIV[-] women who did not receive vaccination (birth cohorts before 1996). Women attending collaborating clinics and the surrounding communities will be recruited by community health care workers and study staff. All women who are interested in the study will meet with a study nurse who will give them an informational flyer and provide a brief verbal description of the study and complete the eligibility screener.

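### The comparison of vaccinated WLWH with vaccinated HIV-negative women is labelled effectiveness, but it reads that way only if type mix does not depend on HIV, an assumption neither stated nor checked

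*Combined protocol and SAP*

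**What the plan says.** Section VII.A.1 notes that the study groups differ in age and possibly in sexual behaviour, and answers this with a ratio: "Therefore, we will use a relative measure of effectiveness to account for the differences in age and possible differences in exposure to HPV". The ratio is the count of HPV6/11/16/18 infections over the count of infections with types for which no cross-protection is expected. It is compared for three pairs: Group 1 (vaccinated WLWH) over Group 2 (unvaccinated WLWH), Group 1 over the group labelled "vaccinated HIV[-] women] (Group 3", and Group 3 over Group 4 (unvaccinated HIV-negative women). The stated justification is: "This will allow us to account for differences in HPV exposure, prevalence, and persistence due to differences in age", together with sexual behaviours. Further models may adjust for age, doses and sexual behaviours.

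The next paragraph carries the effectiveness wording on to comparisons between study groups: "Similarly, exploratory analyses will compare the effectiveness of HPV vaccination for cross-protection types and endpoints of cumulative detection". Earlier in VII.A.1, differences in the prevalence of the type sub-groups "between the four study groups of women will be tested using" Fisher's exact or Pearson chi-square tests.

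In VII.A.2, "Sample size calculation relates to the relative effectiveness measure as discussed", but power is given only for Group 1 against Group 2. Section X.A.1 confirms the comparison of infections "in HPV-vaccinated WLWH to those in unvaccinated WLWH and HPV-vaccinated HIV[-] women". On HIV, section I.A says: "HIV co-infection increases the 1) likelihood of cervical and anal HPV persistence".

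**The concern.** Group 1 over Group 3 contains no vaccinated-versus-unvaccinated contrast. A ratio of targeted to untargeted types cancels anything that acts equally on all types, such as overall exposure or a general rise in persistence. It does not cancel an effect of HIV that differs between targeted and untargeted types. Adjusting for age, doses or sexual behaviours cannot remove such an effect either, because it belongs to HIV itself.

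The documents say that HIV raises HPV persistence. They do not say whether it does so equally for targeted and untargeted types. The limitation in section XI names age differences only. With the present label, a difference in type mix by HIV status could be reported as weaker or stronger vaccine protection in WLWH, or could hide a real difference.

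**Working it through.** **The plan's own figures.** None is given for Group 1 over Group 3. The only Aim 1 power statements (VII.A.2) concern Group 1 against Group 2. Counting one infection per positive woman, the persistence statement does not reproduce: 757 × 0.30 × 0.90 × 0.70 = 143.1 persistent infections per group, of which 80% (114.5) are targeted or untargeted. An OR of 0.5 from 0.3125 to 0.1852 then has 61% two-sided power (72% one-sided), not 80%. That is a separate matter, and nothing below depends on it.

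**Identity.** Let G1 to G4 be the targeted:untargeted ratios in the four groups. Then

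G1/G3 = [(G1/G2) / (G3/G4)] × (G2/G4).

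The bracket is the vaccine OR in WLWH over the vaccine OR in HIV-negative women. The last factor is the type-mix ratio by HIV status without vaccination; write it r2/r4. (As everywhere in this design, Groups 2 and 4 stand in for the vaccinated women had they not been vaccinated.) Any departure of r2/r4 from 1 passes in full into G1/G3. For example, with assumed vaccine effects of 80% in WLWH and 90% in HIV-negative women, the true ratio is 0.2/0.1 = 2.0, but with r2/r4 = 0.6 G1/G3 is 1.2.

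**Illustration: inputs**
- From VII.A.2: 757 per group, 30% prevalence, 25% targeted and 55% untargeted, 10% loss, 70% persistence in WLWH, 36–50% persistence in HIV-negative women.
- Assumed: the same 30% prevalence in HIV-negative women (20% as a variant); vaccine OR 0.4 in both HIV strata (0.2 and 0.1 as variants); infections independent (design effect 1.5 with a robust SE as a variant); r4 from 0.35 to 0.59.

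**Steps**
- r2 = 25/55 = 0.4545. The r4 range is log-symmetric about it: 0.4545²/0.35 = 0.590.
- With equal vaccine effect, G1/G3 = r2/r4, from 0.4545/0.35 = 1.30 to 0.4545/0.590 = 0.77.
- Untargeted prevalent infections per group: 757 × 0.30 × 0.55 = 124.9 (83.3 at 20% prevalence).
- Untargeted persistent infections: 124.9 × 0.90 × 0.70 = 78.7 in WLWH; 124.9 × 0.90 × 0.50 = 56.2 or 124.9 × 0.90 × 0.36 = 40.5 in HIV-negative women.
- Example at r4 = 0.35, OR 0.4, prevalent: targeted counts are 124.9 × 0.4545 × 0.4 = 22.7 and 124.9 × 0.35 × 0.4 = 17.5. SE = √(1/22.7 + 1/124.9 + 1/17.5 + 1/124.9) = 0.342. The shift is ln 1.30 = 0.261, and the two-sided 5% Wald test rejects in 11.9% of studies.

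Rejection of G1/G3 = 1 when vaccine effect is truly equal:

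| Setting | r4 = 0.35 | r4 = r2 | r4 = 0.59 |
|---|---|---|---|
| Prevalent, OR 0.4 | 11.9% | 5.0% | 13.7% |
| Prevalent, OR 0.4, 20% prevalence in HIV-negative | 10.4% | 5.0% | 12.0% |
| Prevalent, OR 0.4, design effect 1.5 | 9.6% | 5.0% | 10.7% |
| Prevalent, OR 0.2 | 8.7% | 5.0% | 9.7% |
| Prevalent, OR 0.1 | 6.9% | 5.0% | 7.4% |
| Persistent, OR 0.4, 50% persistence in HIV-negative | 8.5% | 5.0% | 9.6% |
| Persistent, OR 0.4, 36% persistence in HIV-negative | 7.8% | 5.0% | 8.8% |

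**Precision at r4 = r2, OR 0.4** (CI factor = exp(1.96 × SE), the multiplier either side of the estimate)
- G1/G3: prevalent SE √(2/22.7 + 2/124.9) = 0.323, factor 1.88; persistent SE 0.445 and 0.493, factors 2.39 and 2.63.
- (G1/G2)/(G3/G4): prevalent SE 0.394 (30% prevalence) and 0.441 (20%), factors 2.17 and 2.37; persistent SE 0.544 and 0.602, factors 2.90 and 3.26. With design effect 1.5 the four factors become 2.58, 2.88, 3.69 and 4.25.
- Power of G2 against G4 to detect a mix ratio of 1.30 or 0.77: 16–23% for prevalent and 11–14% for persistent infection.

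**The case against.** The strongest reply is that the misreading is inferred. The effectiveness label is used once, in general terms, and the plan then says only that ratios will be compared. No hypothesis, decision rule or power attaches to Group 1 over Group 3, and X.A.1 speaks of comparing infections. Targeted and untargeted prevalence will be reported with confidence intervals in all four groups. Since G1/G2, G3/G4 and G1/G3 are all planned, a reader can derive both the ratio of ratios and G2/G4 as point estimates. No type-specific HIV effect is shown, and the r4 range is assumed. At a vaccine OR of 0.1, closer to the near-complete protection that the Executive Summary describes for the general population, the rejection rate is only 5–7%. The proposed contrast is imprecise and needs an assumption of its own.

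Much of this stands. The bias is hypothetical, modest in the illustration, and smaller than the sampling error. Rejecting G1/G3 = 1 would also be correct as a statement about type mix. What does not stand is the suggestion that nothing is missing. The text puts the comparison under effectiveness, the condition for that reading appears nowhere, and the four-group tests are on prevalence: both sub-groups could be more prevalent in WLWH with an identical mix. A point estimate that a reader must derive, without an interval, is not a planned analysis.

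**Conclusion.** The concern holds. Group 1 over Group 3 is a valid description of type mix among vaccinated women. It compares vaccine effectiveness only if WLWH and HIV-negative women would have the same targeted:untargeted mix without vaccination. The identity is exact and rests on no assumed number.

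The size is unknown, because the documents give no type mix by HIV status. The illustrated shift and rejection rates rest on an assumed mix and prevalence in HIV-negative women, an assumed equal vaccine OR and, except in the design-effect row, independent infections. They show what could happen, not what will. Group 1 over Group 2, the only powered Aim 1 contrast, and Group 3 over Group 4 are unaffected. The change should be made because the comparison is a stated one, but the main result does not depend on it.

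**What to change.** 1. In VII.A.1, label Group 1 over Group 3 as a comparison among vaccinated women. State that reading it as relative effectiveness requires an equal targeted:untargeted mix by HIV status without vaccination.
2. Add (G1/G2)/(G3/G4), the vaccination-by-HIV ratio of ratios, as a secondary estimate with a 95% CI. Take it from one four-group model that allows for several infections per woman, for example GEE, which VII.C already uses.
3. Report G2 over G4 on the same ratio with a 95% CI, as a check on type mix.
4. State the assumption behind the ratio of ratios. By Table 3, Groups 2 and 4 were born in 1993–1995 and Groups 1 and 3 in 1996–2005, so any age or cohort shift in type mix must be equal in both HIV strata. Group 1 over Group 3 does not need this, so present the two side by side and do not replace one with the other.
5. State that a non-significant result on either added estimate is not evidence of equal effectiveness or equal mix.

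The cost is one extra model and a few sentences. No new data or recruitment is needed. The drawback is the wide intervals and the weak check shown in the working.
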